5.3 General Concomitant Medication and Supportive Care Guidelines

5.3.1 Prophylaxis of Tumor Lysis Syndrome (TLS)

Patients who receive therapy for NHL and CLL are at risk for tumor lysis syndrome (TLS). TLS is an oncologic emergency that can occur spontaneously and/or after treatment in malignant conditions, particularly lymphomas and leukemias. These complications are caused by the breakdown products of dying malignant cells and include hyperkalemia, hyperphosphatemia, hyperuricemia and hypocalcemia, and, if left untreated, acute renal failure.

TLS definitions [42]

Grade 3 (present but not life-threatening): Occurrence of two or more of the following serum values after anticancer treatment:

- i. Uric acid: increase by more than 25% from baseline, or values ≥ 8 mg/dL;
- ii. Potassium: increase by more than 25% from baseline, or values ≥ 6.0 mmol/L;
- iii. Phosphorus: increase by more than 25% from baseline, or values ≥ 4.5 mg/dL;
- iv. Calcium: decrease by more than 25% from baseline, or values ≤ 7 mg/dL.

Grade 4: a life-threatening and/or requiring immediate intervention such as but not limited to new renal failure requiring hemodialysis, or decrease in estimated creatinine clearance (eCrCL) of $>50\%$; symptomatic cardiac arrhythmias incompletely controlled or controlled using a device (defibrillator); any seizure.

Certain patients (for example, those with $WBC > 50,000$ and/or hepatosplenomegaly and/or renal dysfunction [$CrCL < 70$ mL/min] and/or pretreatment hyperuricemia) are at an increased risk of developing TLS.

All patients enrolled on this study will receive the following supportive care:

IV hydration on C1D1 (prior to administration of obinutuzumab). Patients will be encouraged to hydrate orally prior to C1D1 of therapy, aiming to consume >2 L of liquids per day. On day 1 of treatment, patients will receive IV hydration with 0.9% sodium chloride OR D5W with 100 mEq of sodium bicarbonate per 1 Liter at 250 mL/hour beginning at least 1 hour prior to the first dose of obinutuzumab. Hydration will continue for at least 2 hours. The rate of hydration may be adjusted by the Investigator depending on the clinical situation. Diuretics (such as furosemide IV or PO) may be given if deemed necessary.

Allopurinol 300 mg PO daily (or renally adjusted dose, per treating physician). Patients will start taking allopurinol at least 3 days prior to the first dose of entospletinib (day -7) and continue for at least 14 days.

CBC and serum biochemistry/metabolic panel will be measured on C1D1, C1D2, C1D8 and C1D15. Optional serum biochemistry/metabolic panel measurements may be considered by the investigator at the end of C1D1 and C1D2.

Patients whose blood uric acid level exceeds 8.0 mg/dL on C1D1 or C1D2, and who are high risk in the investigator's clinical judgement (i.e., have high tumor burden, high circulating lymphocyte count [$> 25 \times 10^9/L$] or renal impairment), should be given IV rasburicase (3 mg for patients who weigh < 100 kg; 6 mg for patients who weight > 100 kg). Uric acid levels will be measured 2 hours after rasburicase is given and every 2 hours thereafter until level is lowered to ≤ 8.0 mg/dL and drug treatments will be delayed. Those measurements should occur in a chilled heparinized tube, delivered to the laboratory and analyzed STAT. Rasburicase treatment should be repeated if uric acid levels do not decrease by at least 50% within 6 hours and may be repeated at the discretion of the Investigator thereafter.

Patients whose serum potassium exceeds 5 mmol/L will receive 30 g of Kayexalate, additional 1 liter fluid bolus and 20-40 mg of IV furosemide (at the discretion of the Investigator). Potassium levels will be rechecked STAT 1 hour later and every 2 hours thereafter until serum levels are ≤ 5 mmol/L.

5.3.2. Risks Associated with obinutuzumab therapy

Important risks identified in clinical investigations with obinutuzumab were: IRRs, TLS, thrombocytopenia (including acute thrombocytopenia), neutropenia (including prolonged and late onset neutropenia), Protocol Version 10.0 – February 5, 2021

prolonged B-cell depletion, infections (including hepatitis B reactivation and PML), worsening of pre-existing cardiac conditions and GI perforation. See the Obinutuzumab IB for additional details.

5.3.2.1. Hepatitis B Reactivation

Hepatitis B virus (HBV) reactivation, in some cases resulting in fulminant hepatitis, hepatic failure, and death, can occur in patients treated with anti-CD20 antibodies such as obinutuzumab. HBV reactivation has been reported in patients who are hepatitis B surface antigen (HBsAg) positive and also in patients who are HBsAg negative but are hepatitis B core antibody (anti-HBc) positive. Reactivation has also occurred in patients who appear to have resolved hepatitis B infection (i.e., HBsAg negative, anti-HBc positive, and hepatitis B surface antibody [anti-HBs] positive). HBV reactivation is defined as an abrupt increase in HBV replication manifesting as a rapid increase in serum HBV DNA level or detection of HBsAg in a person who was previously HBsAg negative and anti-HBc positive. Reactivation of HBV replication is often followed by hepatitis, i.e., increase in transaminase levels and, in severe cases, increase in bilirubin levels, liver failure, and death.

Positive serology for Hepatitis B is defined as positivity for Hepatitis B surface antigen (HBsAg) or Hepatitis B core antibody (anti-HBc). Screen all patients for HBV infection by measuring HBsAg and anti-HBc before initiating treatment with obinutuzumab. For patients who show evidence of hepatitis B infection (HBsAg positive [regardless of antibody status] or HBsAg negative but anti-HBc positive), consult physicians with expertise in managing hepatitis B regarding monitoring, and consideration for HBV antiviral therapy.

Monitor patients with evidence of current or prior HBV infection for clinical and laboratory signs of hepatitis or HBV reactivation during and for several months following treatment with obinutuzumab. HBV reactivation has been reported for other CD20-directed cytolytic antibodies following completion of therapy.

In patients who develop reactivation of HBV while receiving obinutuzumab, immediately discontinue obinutuzumab and any concomitant chemotherapy, and institute appropriate treatment. Resumption of obinutuzumab in patients whose HBV reactivation resolves should be discussed with physicians with expertise in managing hepatitis B. Insufficient data exist regarding the safety of resuming obinutuzumab in patients who develop HBV reactivation.

For the subset of patients who are Hepatitis B viral DNA-negative and anti-HBc positive and have undetectable Hepatitis B viral DNA levels at screening, Hepatitis B viral DNA levels must be followed approximately every 4 weeks. Guidelines for the management of hepatitis B reactivation are outlined in Table 1.

Table 4. Management of Hepatitis B Reactivation

Hepatitis B Viral DNA Level by Real-Time PCR	Guideline
> 100 IU/mL	
• Hold obinutuzumab• Begin anti-viral medication and treat for at least 1 year after the last dose of obinutuzumab.• Immediately refer the patient to a gastroenterologist or hepatologist for management.• Resume obinutuzumab once Hepatitis B viral DNA levels decrease to undetectable levels.
> 100 IU/mL while on anti-viral medication	Discontinue obinutuzumab.
29–100 IU/mL	
Retest within 2 weeks.
 
If still hepatitis B viral DNA positive:
 
• Hold obinutuzumab• Begin anti-viral medication and treat for at least 1 year after the last dose of obinutuzumab.• Immediately refer the patient to a gastroenterologist or hepatologist for management• Resume obinutuzumab once Hepatitis B viral DNA levels decrease to undetectable levels

5.3.2.2. Progressive Multifocal Leukoencephalopathy

JC virus infection resulting in progressive multifocal leukoencephalopathy (PML), which can be fatal, was observed in patients treated with obinutuzumab. Consider the diagnosis of PML in any patient presenting with new onset or changes to preexisting neurologic manifestations. Evaluation of PML includes, but is not limited to, consultation with a neurologist, brain magnetic resonance imaging (MRI), and lumbar puncture. Discontinue obinutuzumab therapy and consider discontinuation or reduction of any concomitant chemotherapy or immunosuppressive therapy in patients who develop PML.

5.3.2.3. Infusion-Related Reactions

Obinutuzumab can cause severe and life-threatening IRRs; 65% of patients with CLL experienced a reaction to the first 1000 mg infusion of obinutuzumab, and 38% of iNHL patients experienced a reaction on Day 1 of obinutuzumab infusion. IRRs within 24 hours of receiving obinutuzumab have occurred. IRRs can also occur with subsequent infusions. Symptoms may include hypotension, tachycardia, dyspnea, and respiratory symptoms (e.g., bronchospasm, larynx and throat irritation, wheezing, and laryngeal edema). Most frequently reported symptoms include nausea, fatigue, dizziness, vomiting, diarrhea, hypertension, flushing, headache, pyrexia, and chills.

Medications (including subcutaneous epinephrine, corticosteroids, and intravenous diphenhydramine) and resuscitation equipment should be available for immediate use.

For patients with preexisting cardiac or pulmonary conditions, monitor more frequently throughout the infusion and the post-infusion period because patients may be at greater risk of experiencing more severe reactions. Hypotension may occur as part of the obinutuzumab IRR. Consider withholding antihypertensive treatments for 12 hours prior to administration, during each obinutuzumab infusion, and for the first hour

after administration until blood pressure is stable. For patients at increased risk of hypertensive crisis, consider the benefits versus the risks of withholding antihypertensive medication as suggested above.

Certain patients are at risk and need to be closely monitored: those with pre-existing cardiac or pulmonary conditions, those who experienced prior cardiopulmonary adverse reactions, and those with high numbers of circulating malignant cells ($>25,000/\text{mm}^3$). This protocol prescribes a divided dose of obinutuzumab in all patients (100 mg on day 1 and 900 mg on day 2).

Institutional guidelines may be used for obinutuzumab administration. We suggest this general approach: vital signs should be taken every 15 minutes for the first hour of infusion until stable, then every 30 minutes until the completion of infusion. Pulse oximetry on room air should be performed at baseline and as needed if dyspnea occurs. Epinephrine 1 mg/ml, diphenhydramine 50 mg IV and hydrocortisone 100 mg IV should be readily available during obinutuzumab infusion. For first infusion (C1D1), obinutuzumab is administered at a rate of 25 mg/hour for four hours. On C1D2 obinutuzumab is started at 25 mg/hr (50 mg/hr if no IRR occurred on C1D1) and rate escalated by 50 mg/hour every 30 minutes until a maximum rate of 400 mg/hour provided no infusion reaction occurs. For subsequent infusions, infusion may be started at 50 mg/hour (100 mg/hour if no reactions with previous infusion) and increased by 100 mg/hour increments every 30 minutes until a maximum rate of 400 mg/hour.

If a patient experiences an infusion reaction of any grade during infusion, adjust the infusion as follows:

Grade 4 (life threatening): Stop infusion immediately and permanently discontinue obinutuzumab therapy.

Grade 3 (severe): Interrupt infusion and manage symptoms. Upon resolution of symptoms, consider restarting obinutuzumab infusion at no more than half the previous rate (the rate being used at the time that the infusion reaction occurred) and, if patient does not experience any further infusion reaction symptoms, infusion rate escalation may resume at the increments and intervals as appropriate for the treatment cycle dose. Permanently discontinue obinutuzumab treatment if patients experience a Grade 3 infusion-related symptom at re-challenge.

For CLL patients only, the Day 1 infusion rate may be increased back up to 25 mg/hr after 1 hour but not increased further.

Grade 1 – 2 (mild to moderate): Reduce infusion rate or interrupt infusion and treat symptoms. Upon resolution of symptoms, continue or resume infusion and, if patient does not experience any further infusion reaction symptoms, infusion rate escalation may resume at the increments and intervals as appropriate for the treatment cycle dose.

For CLL patients only, the Day 1 infusion rate may be increased back up to 25 mg/hr after 1 hour but not increased further.

Any overdose or incorrect administration of study drug should be noted in the medical chart. Adverse events associated with an overdose or incorrect administration of study drug should be reported.

For fevers, chills and rigors demerol 12.5 mg IV may be administered and repeated every 15 minutes up to a maximum dose of 50 mg. For severe dyspnea and bronchospasm, administer 100 mg hydrocortisone IV and/or 50 mg benadryl IV. In an emergent situation give epinephrine 0.3 mg/0.3 ml IM. For systolic blood pressure ≤ 80 mm Hg infuse 0.9% sodium chloride at 250 ml/hr, check blood pressure at least every 10 minutes until it reaches baseline $\pm 10\%$. After symptoms have resolved resume the infusion at 50% the previous rate and increase as above, or at 10 mg/hr every 15 minutes (if severe reaction observed).

Premedication to reduce the risk of infusion reactions is outlined in Table 5.

Table 5. Obinutuzumab Dosing Schedule for Six 28-Day Treatment Cycles for Patients with CLL and NHL

Day of Treatment Cycle	Patients Requiring Premedication	Premedication	Administration
Cycle 1 Days 1 and 2	All patients	Intravenous glucocorticoid: 20 mg dexamethasone or 80 mg methylprednisolone	Completed at least 1 hour prior to obinutuzumab infusion.
		650–1000 mg PO acetaminophen	At least 30 minutes before obinutuzumab infusion.
		anti-histamine (e.g., 50 mg diphenhydramine IV/ PO)	
All subsequent cycles	All patients	650–1000 mg PO acetaminophen	At least 30 minutes before obinutuzumab infusion.
	Patients with an IRR (Grade 1-2) with the previous infusion	650–1000 mg PO acetaminophen	At least 30 minutes before obinutuzumab infusion.
		anti-histamine (e.g., 50 mg diphenhydramine IV/PO)	
	Patients with a Grade 3 IRR with the previous infusion OR with a lymphocyte count $> 25 \times 10^9/L$ prior to next treatment	Intravenous glucocorticoid: 20 mg dexamethasone or 80 mg methylprednisolone	Completed at least 1 hour prior to obinutuzumab infusion.

5.3.2.4. Infections

Serious, bacterial, fungal, and new or reactivated viral infections can occur during and following the completion of obinutuzumab therapy. Fatal infections have been reported. Do not administer obinutuzumab to patients with an active infection. Patients with a history of recurring or chronic infections may be at increased risk of infection.

5.3.2.5. TLS with obinutuzumab

TLS, including fatal cases, has been reported in patients receiving obinutuzumab. Patients with high tumor burden, high circulating lymphocyte count ($> 25 \times 10^9/L$) or renal impairment are at greater risk for TLS and should receive appropriate tumor lysis prophylaxis with anti-hyperuricemics (e.g., allopurinol or rasburicase) and hydration prior to the infusion of obinutuzumab. Continue prophylaxis prior to each subsequent obinutuzumab infusion, as needed. See section 5.3.1 for detailed recommendations on management of TLS.

During the initial days of obinutuzumab treatment, monitor the laboratory parameters of patients considered at risk for TLS. For treatment of TLS, correct electrolyte abnormalities, monitor renal function and fluid balance, and administer supportive care, including dialysis as indicated.

For patients with evidence of TLS, obinutuzumab should be discontinued and the patient treated as clinically indicated. Following the complete resolution of TLS complications, obinutuzumab may be re-administered at the full dose during the next infusion in conjunction with prophylactic therapy.

5.3.2.6. Hematologic Toxicities

Neutropenia

Severe and life threatening neutropenia, including febrile neutropenia, has been reported during treatment with obinutuzumab. Patients with Grade 3–4 neutropenia should be monitored frequently with regular laboratory tests until resolution. Anticipate, evaluate, and treat any symptoms or signs of developing infection (see Section 6.1 for management of neutropenia). Consider administration of granulocyte colony-stimulating factors (G-CSF) in patients with Grade 3 or 4 neutropenia (outside of the DLT window).

Neutropenia can also be of late onset (occurring more than 28 days after completion of treatment) and/or prolonged (lasting longer than 28 days).

Dose delays may be considered in the case of Grade 3 or 4 neutropenia. Patients with severe and long lasting (>1 week) neutropenia are strongly recommended to receive antimicrobial prophylaxis until resolution of neutropenia to Grade 1 or 2. Antiviral and antifungal prophylaxis should be considered.

Thrombocytopenia

Severe and life threatening thrombocytopenia has been reported during treatment with obinutuzumab in combination with chlorambucil or bendamustine. Fatal hemorrhagic events during Cycle 1 have also been reported in patients with CLL treated with obinutuzumab.

Monitor all patients frequently for thrombocytopenia and hemorrhagic events, especially during the first cycle. In patients with Grade 3 or 4 thrombocytopenia, monitor platelet counts more frequently until resolution (see Section 6.1 for management of thrombocytopenia). Transfusion of blood products (i.e., platelet transfusion) may be necessary. Consider withholding concomitant medications which may increase bleeding risk (platelet inhibitors, anticoagulants), especially during the first cycle.

Hematological Toxicities in Patients with CLL

The evaluation of potential treatment-induced toxicity in patients with advanced CLL may be quite difficult and requires careful consideration of both the manifestations of the underlying disease, as well as adverse reactions to the therapy under study. Some of the conventional criteria for toxicity are not applicable, especially under circumstances of progressive bone marrow failure from the CLL itself.

Dose modifications for hematologic toxicity in patients with CLL must be made with consideration of the increased frequency of hematologic compromise at the initiation of therapy. Therefore, the standard criteria used for solid tumors are difficult to be applied directly; many patients would be considered to have Grade 2–4 hematologic toxicity at presentation.

As a consequence, dose modification decisions for patients with cytopenia (below the lower limit of the normal range) at baseline will be based on the NCI sponsored Working Group (NCI-WG) grading scale for hematologic toxicity in CLL studies.

5.3.2.7. Immunization

The safety and efficacy of immunization with live or attenuated viral vaccines during or following obinutuzumab therapy have not been studied. Immunization with live-virus vaccines is not recommended during treatment and until B-cell recovery.

5.3.3. CYP Inhibitors and Inducers

In vitro data indicates that entospletinib is a substrate of CYP2C9 and to a lesser extent CYP3A. Co-administration of CYP2C9 inhibitors or CYP2C9 or CYP3A inducers may increase or decrease entospletinib exposure, respectively. As such, coadministration of moderate and strong CYP3A and CYP2C9 inducers, and strong CYP2C9 inhibitors is prohibited in this study.

Caution should be exercised when coadministering drugs that are moderate inhibitors of CYP2C9 (e.g., flucconazole, voriconazole, and amiodarone). Administration of strong and moderate CYP3A and CYP2C9 inducers and strong CYP2C9 inhibitors is also prohibited for 2 weeks prior to study drug

administration. Examples of strong CYP2C9 inhibitors and strong/moderate inducers are provided in Appendix 3.

In vitro data indicates that entospletinib has the potential to inhibit several transporters and the metabolizing enzyme UGT1A1, which may affect the plasma concentrations of substrates of these transporters and/or enzyme. Caution should be exercised when coadministering medications that are metabolized or transported by UGT1A1, OATP1B1, OATP1B3, MATE1, P-gp, and BCRP, such as rosuvastatin and atorvastatin. The investigator should review the prescribing information of the concomitant medication for guidance on co-administration with an inhibitor of these transporters, such as additional monitoring, dose modifications or avoiding co-administration. In a study in healthy volunteers, entospletinib 400 mg twice daily increased rosuvastatin exposure by approximately 3.3-fold; as such the following restrictions apply for subjects receiving entospletinib in this study: atorvastatin, pravastatin, simvastatin, lovastatin and fluvastatin dose needs to be limited to 20 mg daily; rosuvastatin – to 10 mg daily.

5.3.4. Proton Pump Inhibitors

Studies in healthy volunteers have demonstrated a significant reduction in entospletinib exposure when proton pump inhibitors are co-administered. Therefore, proton pump inhibitors (e.g., omeprazole, esomeprazole, pantoprazole, lansoprazole, rabeprazole) are prohibited in combination with entospletinib. H2 antagonists are allowed.

5.3.5. QT Prolonging Agents

Neither entospletinib nor obinutuzumab have been shown to prolong QT interval. However, any medications known to cause QT prolongation should be used with caution; periodic monitoring with ECGs and electrolytes should be considered.

5.3.6. Growth Factors

Patients may receive filgrastim, peg-filgrastim, erythropoietin or related growth factors at the discretion of the treating physician. Growth factors cannot be administered within the DLT window.

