Patients with HCL must be intolerant of or not candidates for purine analog-based therapy, or failed to achieve response (CR or PR) or relapsed within 2 years of such therapy, AND meet the standard treatment initiation criteria (ANC $\leq 1000/\mu\text{L}$, Hgb $\leq 10 \text{ g/dL}$, platelet count $\leq 100,000/\mu\text{L}$).

Patients with indolent lymphoma (FL, LPL, MZL) and patients with B-cell prolymphocytic leukemia must have an indication for treatment in the opinion of the investigator.

Patients with MCL and patients with CLL in Richter's transformation should have previously received or not be candidates for high dose chemotherapy/autologous stem cell transplant.

3.1.4 For diseases other than CLL, LPL, and HCL, presence of radiographically measurable lymphadenopathy or extra-nodal lymphoid malignancy (defined as the presence of ≥ 1 lesion that measures ≥ 2.0 cm in the longest dimension [LD] and ≥ 1.0 cm in the longest perpendicular dimension [LPD] as assessed by CT or MRI). For LPL, measurable disease will be defined as serum monoclonal IgM $> 0.5 \text{ g/dL}$ or meeting at least 1 of the recommendations from the Second International Workshop on LPL for requiring treatment (Appendix E).

3.1.4 Patients must have ECOG performance status ≤ 2 (Refer to Appendix D).

3.1.5 Patients must have organ function as defined below:

- i) direct bilirubin $\leq 2 \times$ institutional ULN (unless due to known Gilbert's syndrome or compensated hemolysis directly attributable to CLL)
- ii) AST or ALT less than $2.5 \times$ institutional ULN
- iii) estimated CrCL using the Cockcroft-Gault equation $\geq 50 \text{ mL/min}$ (see Appendix B).
- iv) platelets $\geq 50,000/\text{mm}^3$ independent of transfusion support, with no active bleeding, and absolute neutrophil count (ANC) $\geq 1000/\text{mm}^3$, unless due to disease involvement in the bone marrow.

3.1.6 Ability to understand and the willingness to sign a written informed consent document.

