5.2 Definition of Dose-Limiting Toxicities (DLT)

Dose escalation will stop for DLT defined as any of the following occurring with cycle 1 (including run-in) in the dose escalation phase, deemed related (possibly, probably or definitely) to the study drug:

1. Non-hematologic toxicity: all \geq Grade 3 toxicities *except*
 - a. Grade 3 nausea, vomiting or diarrhea reversible within 72 h with supportive care
 - b. Grade 3 infusion-related toxicity
 - c. Asymptomatic Grade 3-4 laboratory abnormalities that are reversible to \leq Grade 2 within 72 hours (for example, Grade 3-4 elevation of uric acid, AST, ALT, changes in phosphorus and magnesium levels, changes in glucose levels)
 - d. Grade 3 only: tumor lysis syndrome (TLS) or hyponatremia (equals Na 120-130 mEq/L)
2. Hematologic toxicity:
 - a. Grade 4 neutropenia lasting more than 7 days in a subject with ANC $> 1500 \mu\text{L}$ before beginning therapy
 - b. Febrile neutropenia of any duration (ANC $< 500/\mu\text{L}$, fever $> 38.5^\circ\text{C}$)
 - c. Grade 4 thrombocytopenia/anemia or grade 3 thrombocytopenia with bleeding or any requirement for platelet transfusion, unexplained by underlying disease

Grading of toxicities will be according to NCI CTCAE v.4.03. Grading of hematologic toxicity in patients with CLL/SLL will be conducted according to the 1996 modified NCI-WG criteria for CLL/small lymphocytic lymphoma (SLL), updated in 2008 [41]. A toxicity deemed to be unrelated to therapy (such as hip fracture due to a traumatic fall), will NOT be considered as a DLT.

Patients who completed 1 cycle of study treatment will be evaluable for dose escalation decision purpose. Patients who receive $< 50\%$ of doses of entospletinib or < 2 doses of obinutuzumab during cycle 1 and who do not experience DLT, will NOT be evaluable for dose escalation decision purpose and will be replaced. Intra-patient dose escalation will be allowed to the level of MTD, once MTD has been determined.

Management and dose modifications associated with the above adverse events are outlined in Section 6.

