6.0 DOSING DELAYS/DOSE MODIFICATIONS

6.1 Dose Modifications/Delays for Toxicities Encountered During Therapy.

Table 6. Dose Modifications and Delays for Entospletinib and Obinutuzumab

Description		Grade	Dose modification
Non-hematologic	Initial or first recurrence	3-4 and clinically significant*	Hold treatment with both drugs and evaluate at least weekly as clinically indicated. Delay dose until toxicity resolves to Grade ≤ 2 , then complete current cycle or start next cycle with reduction in entospletinib by one dose level (Table 5)
	Second recurrence		Discontinue
Description		Grade	Dose modification
Hematologic	Initial or first recurrence	As defined in DLTs: Grade 4 neutropenia lasting > 7 days. Grade 4 thrombocytopenia/ anemia or grade 3 thrombocytopenia with bleeding or any requirement for platelet transfusion, unexplained by underlying disease Febrile neutropenia	Hold treatment with both drugs. Initiate at least weekly CBC checks, growth factor (G-CSF allowed at Investigator's discretion) and transfusion support as clinically indicated until resolved to Grade 1 or $> 75\%$ baseline. May continue this cycle or start next cycle with reduction in entospletinib by one dose level (Table 5).
	Second recurrence		Discontinue

*Not clinically significant includes: Grade 3 nausea or vomiting occurring without optimal treatment; asymptomatic Grade 3 laboratory abnormalities that are not life-threatening and respond to treatment; grade 3 obinutuzumab infusion reactions; grade 4 infusion reaction, which will be an investigator dependent decision

Note: Grading of non-hematologic toxicities will be according to NCI CTCAE v.4.03. Grading of hematologic toxicity will be according to the 1996 modified NCI-WG criteria for CLL/SLL, updated in 2008.

Table 7. Restarting Doses of Entospletinib after Treatment Interruption for Drug-Related Toxicity

Entospletinib dose at the time of first toxicity	1 st reduction	2 nd reduction
200 mg daily	Discontinue	-
200 mg BID	200 mg daily	Discontinue
400 mg BID	200 mg BID	200 mg daily

There are NO dose reductions for obinutuzumab.

In cases where toxicities led to dose reduction, dose re-escalation of entospletinib may be considered in subsequent cycles at the discretion of the treating physician after at least two cycles of study therapy are well tolerated without any recurrent toxicities at the reduced dose.

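### The growth-factor ban in 5.3.6 has no end point, so it still bars G-CSF after a neutropenic DLT has been documented, when it no longer protects the 3+3 decision

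*Combined protocol and SAP*

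**What the plan says.** Four places in the combined protocol and SAP bear on this.

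- **Section 5.3.6** leaves growth factors to the treating physician in general, then adds: "Growth factors cannot be administered within the DLT window". No exception follows.
- **Section 5.3.2.6** advises considering G-CSF "in patients with Grade 3 or 4 neutropenia (outside of the DLT window"). This wording is advisory. It comes shortly after a pointer to other text: "see Section 6.1 for management of neutropenia".
- **Section 5.2** defines the hematologic DLTs over cycle 1 including the run-in. They include febrile neutropenia of any duration and "Grade 4 neutropenia lasting more than 7 days in a subject with ANC" above 1500 at the start. A DLT must also be "deemed related (possibly, probably or definitely) to the study drug". The section closes with: "Management and dose modifications associated with the above adverse events are outlined in Section 6".
- **Section 6.1, Table 6** takes the hematologic DLT events as its trigger, orders both drugs held, and continues: "Initiate at least weekly CBC checks, growth factor (G-CSF allowed at" the investigator's discretion). It mentions neither cycle 1 nor the DLT window, and it repeats the neutropenia criterion without the baseline-ANC condition.

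Section 10.2.2 separately permits G-CSF support from cycle 2 onward.

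**The concern.** A reader who follows 5.2 to its management section arrives at a table that allows G-CSF for a cycle-1 DLT. A reader who starts at 5.3.6 finds G-CSF barred for the same patient on the same day. The protocol states no order of precedence and does not say when the ban stops.

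The ban has a clear statistical purpose up to the event. G-CSF given early could bring Grade 4 neutropenia to an end within 7 days, so that a DLT would go uncounted. That purpose is met once the DLT has been documented. From then on, an investigator who obeys 5.3.6 withholds a discretionary treatment for febrile or prolonged neutropenia with no gain for dose finding, and one who uses Table 6 commits a protocol deviation. What is at stake is patient management and consistent instructions to sites.

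**Working it through.** The plan states no figure on this point that could be reproduced. The check has four parts.

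**1. Length of the window.** The protocol does not define the term; I infer it from 5.2 as run-in plus cycle 1. Section 5.1 gives a 7-day run-in and 5.1.1 a 28-day cycle: 7 + 28 = 35 days.

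**2. Days of ban left after the event.** The onset days are assumptions.

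- Febrile neutropenia on cycle-1 day d leaves 28 − d days.
- Grade 4 neutropenia starting on day d passes 7 days on day d + 7, which leaves 28 − (d + 7) = 21 − d days.

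| Onset | Febrile neutropenia | Grade 4 beyond 7 days |
|---|---|---|
| First run-in day | 35 − 1 = 34 | 35 − 8 = 27 |
| C1D1 | 27 | 20 |
| C1D8 | 20 | 13 |
| C1D15 | 13 | 6 |

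These are days on which the ban applies, not days of harm. The ban matters only while neutropenia persists. With the exception proposed below, the days left fall to 0.

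**3. Effect on dose escalation.** Table 3 in 5.1.1 counts participants with a DLT. So does the rule in 13.1 that returns the study to Phase I. With true DLT probability p per patient, the chance of escalating from a dose level is

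(1 − p)³ + 3p(1 − p)² × (1 − p)³.

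- p = 0.10: 0.729 + 0.243 × 0.729 = 0.906
- p = 0.20: 0.512 + 0.384 × 0.512 = 0.709
- p = 0.30: 0.343 + 0.441 × 0.343 = 0.494

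Each patient enters only as yes or no. A patient already scored yes stays yes whatever treatment follows, so lifting the ban at that moment leaves these values as they are.

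**4. How many patients.** The rates come from 2.3.2.2. The 6 to 12 escalation patients come from 5.1.1. Intervals are Clopper-Pearson 95%.

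- *Closest population* (relapsed/refractory CLL, obinutuzumab alone at 1000 mg): related Grade 3–4 febrile neutropenia in 1/20 = 5% (0.1% to 24.9%). Expected cases: 6 × 0.05 = 0.3 and 12 × 0.05 = 0.6. The upper limit would give 6 × 0.249 = 1.5 and 12 × 0.249 = 3.0.
- *Poorer match* (untreated CLL with chemotherapy): 3/21 = 14.3% (3.0% to 36.3%) with FC gives 0.9 to 1.7 cases. The stated 10% of 20 with bendamustine, taken as 2/20 (1.2% to 31.7%), gives 0.6 to 1.2.
- *Grade 4 neutropenia*: 5/13 = 38% (13.9% to 68.4%) at 400–2000 mg gives 2.3 to 4.6 cases as an upper guide. In the closest population, related Grade 3–4 neutropenia was 4/20 = 20%, or 1.2 to 2.4 cases, of which Grade 4 is only a part. Neither source says how many lasted beyond 7 days, so the number meeting the DLT criterion is lower by an unknown amount.

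All these rates cover whole treatment without entospletinib. The documents give no cycle-1 rate for this combination.

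**The case against.** **The texts do not strictly contradict each other.** Table 6 permits and does not require, so a site that withholds G-CSF in the window complies with both. The order of the text in 5.3.2.6, and the permission from cycle 2 in 10.2.2, suggest that the ban was meant to prevail. This stands, and it narrows the point to a missing end of the ban. It does not remove the point, because an investigator who uses the discretion in Table 6 is still in deviation.

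**The window might be read as closed after a DLT.** Sections 7.2 and 13.3 treat a patient who stops early because of a DLT as already evaluable. A site could reason from this, but no text says so, and sites could differ.

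**Harm is limited.** In the 13-patient obinutuzumab cohort in 2.3.2.2, all 3 patients with Grade 3–4 neutropenia who had no G-CSF recovered spontaneously, and infections did not appear more frequent. Drug holds, at least weekly counts and antimicrobial prophylaxis remain available, and 12.5 allows an immediate change to remove an apparent hazard. This stands too. Against it, 6 of the 9 patients with Grade 3–4 neutropenia in that cohort received G-CSF (67%), so investigators are likely to want it.

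**A reader might infer that the ban should also end for every event in Table 6, including those that are not DLTs.** The documents do not support this. Section 3.1.5 admits patients with ANC down to 1000, or lower where marrow disease is the cause (the limit applies "unless due to disease involvement in the bone marrow"). With a baseline of 1500 or less they cannot meet the neutropenia-duration DLT. They can still have a febrile-neutropenia DLT, or a related infection of Grade 3 or higher, which 5.2 does not exempt. The same holds for a patient whose event was judged unrelated. G-CSF could mask such a later DLT and tilt the count toward escalation.

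**Conclusion.** The point holds for patients with a documented DLT of febrile neutropenia or of Grade 4 neutropenia beyond 7 days. For them the ban in 5.3.6 outlives its purpose and conflicts with the discretion that Table 6 gives.

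The size is small: about 0.3 to 0.6 febrile-neutropenia cases in 6 to 12 patients on the closest data, with a wide interval, plus an unknown number with prolonged Grade 4 neutropenia. This assumes that the window is run-in plus cycle 1, and that whole-treatment rates for obinutuzumab alone are a rough guide to the combination.

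A reader might infer that the gap biases the DLT count or the MTD. It does not: the 3+3 rule counts patients, and the ban before the event is sound. Nor do the documents show that the ban has a large clinical cost. This is a low-cost correction for patient management and protocol consistency.

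**What to change.** Amend 5.3.6 to read, for example: *Growth factors may not be given within the DLT window (run-in and cycle 1), except that once febrile neutropenia, or Grade 4 neutropenia beyond 7 days, has been documented as a DLT in a patient, therapeutic G-CSF is allowed for that patient per Table 6.* Align the parenthesis in 5.3.2.6 with this sentence, and add a cross-reference to it in Table 6. The sentence also fixes the meaning of the window, which the protocol now leaves to inference.

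Keep the ban for patients without a documented DLT, including those with baseline ANC of 1500 or less and those whose event is judged unrelated. Relaxing it there would trade patient management against DLT ascertainment. That is a separate decision.

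The cost is one exception, one aligned phrase and one cross-reference, made through the amendment route in 12.5. No new data are needed, because 10.4 already requires concomitant treatments in the CRF. The 3+3 rules and the DLT definitions stay as they are.
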